9.6.1 Objective Response Rate

The ORR is the proportion of patients who achieve a response of either CR or PR. ORR will be summarized and 95% Clopper Pearson confidence interval will be reported for each dose or analysis group.

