8.2 Response Evaluation and Criteria

NOTE: As of Amendment 9, Section 8.2 and its subsections (8.2.1, 8.2.1.1, and 8.2.1.2) are no longer applicable. All disease response assessments, including the timing, type, and evaluation of imaging, are to be performed and assessed per the Investigator based on local standard of care; the data will not be collected and no longer need to be recorded in the CRF. Confirmation of progression by repeat imaging is not mandatory. Decisions on treatment discontinuation should be made per Investigator based on local standard of care and in accordance with the stopping rules outlined in Section 9.2. The text in these sections is retained as a reference only to aid Investigators in making treatment decisions and is not mandatory.

All baseline efficacy evaluations will be performed at Screening. Baseline radiographic and superficial measurement (as applicable for superficial lesions) must be performed no more than 4 weeks prior to study enrollment. The same imaging method used at baseline should be used throughout the study unless a change is required due to AEs (eg, new radiographic contrast allergy) per local radiology guidelines.

Evaluation of superficial lesions requires both photographic and manual (caliper) measurement at all time points that radiographic imaging is required per Schedule of Trial Events ([Appendix 1](#) through [Appendix 4](#)). Although radiographic imaging collected at the scheduled time points is preferred, it is allowed to be obtained the day prior to study treatment.

Response to treatment and disease progression will be evaluated by the investigator and recorded on the CRF every 9 weeks after the first trial injection until Day 379 and then every 12 weeks thereafter for the remainder of the trial. All treatment response and disease progression require confirmation of response (complete response [CR] or partial response [PR]) using RECIST v1.1 and irRECIST, which is the study-specific irRECIST that requires confirmation of disease progression with an additional scan obtained at least 4 weeks later that also meets the criteria of PD per RECIST v1.1 ([Appendix 6](#), Immune-related RECIST). Patients with suspected disease progression should continue to follow trial procedures until they have confirmed disease

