1.0 INTRODUCTION

This statistical analysis plan contains definitions of analysis populations and endpoints, outlines the timing of statistical analyses, and provides a comprehensive description of statistical analyses to be implemented to assess the safety, tolerability, biologic activity, and preliminary efficacy of SD-101 in combination with pembrolizumab as described in Protocol DV3-MEL-01 (Amendment 8: 08 February 2018): “A Phase 1b/2, Open-label, Multicenter, Dose escalation and Expansion Trial of Intratumoral SD-101 in Combination With Pembrolizumab in Patients With Metastatic Melanoma or Recurrent or Metastatic Head and Neck Squamous Cell Carcinoma (HNSCC)”.

Due to strategic changes, only some of the objectives will be evaluated. Those objectives not evaluated will be *italicized* and annotated as “*(not implemented)*”, where applicable, throughout this SAP; statistical methods for these objectives are also not described. The main text of this SAP covers only assessment of the objectives by data contained in the clinical database. Pharmacodynamic assessment will be described in an annex to this SAP. Pharmacodynamic objectives will also be annotated.

Groupings of patients to be used in the analyses are also changed from what were described in the protocol, based on the knowledge accumulated through the conduct of the trial.

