9.6 Efficacy Analyses

Response of lesions and disease status will be assessed using standard RECIST v1.1 for the primary evaluation of response *and a study specific modified RECIST v1.1 referred to as immune related-RECIST v1.1 (irRECIST v1.1) for an exploratory evaluation (not implemented)*. Therefore, RECIST v1.1 will be used with the following adaptations (Appendix 1):

- Determination of progressive disease (PD) requires a confirmation of PD by imaging ≥ 4 weeks later. In order to confirm PD, both the initial lesion assessment and lesion assessment on the confirmatory scan must meet PD criteria ($\geq 20\%$ increase in sum of diameters).
- Continued treatment while awaiting radiologic confirmation of progression is encouraged if the patient is stable.

Patients that are deemed clinically unstable are not required to have repeat imaging for the confirmation of PD.

Objective response rate (ORR) and disease control rate (DCR) will be evaluated for injected and non-injected lesions as well as for all target lesions. The ORR will include patients with complete response (CR) or partial response (PR). The DCR will include patients with CR, PR, or stable disease. The ORR and DCR will be determined by Investigator using RECIST v1.1.

Unless otherwise specified, all efficacy analyses will be performed by:

- Lesion type – injected, non-injected lesions, all target lesions

- Evaluation criteria – RECIST v1.1
- Study Phase – Phase 1 by dose groups, Phase 2 by analysis groups

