9.6.2 Best Overall Response

The best overall response rate (BORR) is the proportion of patients who achieve a best response recorded at any post-baseline assessment. BORR will be summarized and 95% Clopper Pearson confidence interval will be reported for each dose or analysis group.

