9.6.5 Duration of Response

The duration of response is defined as the period of time from the date of initial confirmed PR or CR until the date of PD or death, whichever is earlier. For those patients who achieved response, duration of response will be summarized descriptively. Kaplan-Meier estimate of median duration and 95% confidence interval will be provided.

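### The SAP sets no confirmation requirement for the primary ORR, although Protocol 8.2 and the SAP's own duration-of-response definition rest on confirmed CR/PR

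*SAP*

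**What the plan says.** The response rules in the two documents are these:

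- **ORR, SAP 9.6.1:** "The ORR is the proportion of patients who achieve a response of either CR or PR". SAP 9.6 adds the assessor: "The ORR and DCR will be determined by Investigator using RECIST v1.1". Neither place mentions confirmation, and the RECIST appendix to the SAP defines CR and PR without a confirmation step.
- **Best overall response, SAP 9.6.2:** "proportion of patients who achieve a best response recorded at any post-baseline assessment".
- **Time to response, SAP 9.6.4:** runs from first SD-101 dose to onset of CR or PR, with no mention of confirmation.
- **Duration of response, SAP 9.6.5:** "the period of time from the date of initial confirmed PR or CR until the date of PD or death". The same section then summarizes duration for patients who achieved response, without restricting that set to confirmed responders.
- **Progression, SAP 9.6:** "Determination of progressive disease (PD) requires a confirmation of PD by imaging ≥ 4 weeks later". This is the only confirmation rule with an interval in the SAP's efficacy section.
- **Protocol 8.2:** "All treatment response and disease progression require confirmation of response (complete response [CR] or partial response [PR]) using RECIST v1.1 and irRECIST". The Amendment 9 note at the head of that section makes it no longer applicable: "The text in these sections is retained as a reference only to aid Investigators in making treatment decisions and is not mandatory".
- **Protocol 12.8:** defines ORR by a best response of CR or PR, without the word confirmed, and starts duration at a confirmed response.

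SAP 1.0 says it is written to Amendment 8. Protocol 8.2.1.1 allows ORR and DCR to be analysed on data collected before Amendment 9.

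**The concern.** ORR is the Phase 2 primary endpoint of an open-label trial without randomization, and the investigator reads the response. In that setting a second assessment is a main guard against measurement error around the 30% threshold for PR. If the SAP does not say whether that guard applies, the choice can be made at programming, when the open-label responses are already known.

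There is also an internal problem that does not depend on the protocol. ORR, time to response and duration of response should describe one set of responders. As written, the first two need a CR or PR and the third needs a confirmed one, while its summary set is everyone who responded.

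**Working it through.** **1. The plan's own figures.** Exact binomial, inputs from SAP 5.0.

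- Cohort 1: n = 60, null 35%, alternative 55%, one-sided 0.05. P(X ≥ 27 | 60, 0.35) = 0.070 and P(X ≥ 28 | 60, 0.35) = 0.041, so the threshold is 28. Power is P(X ≥ 28 | 60, 0.55) = 0.923, which agrees with the stated power above 90%.
- Cohort 2: n = 25, null 10%, threshold 6, alternative 30%. P(X ≥ 6 | 25, 0.10) = 0.033 and P(X ≥ 6 | 25, 0.30) = 0.807, which agrees with the stated 80% power.

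Requiring confirmation changes none of these, provided the planning rates refer to confirmed responses. The documents do not say whether they do.

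**2. One patient followed through the rules.** Take a PR at the first scan (Day 64) that is not met at the next scheduled scan 9 weeks later (Day 64 + 63 = Day 127).

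| Rule | Result for this patient |
|---|---|
| SAP 9.6.1, ORR | counts, read literally |
| SAP 9.6.2, best response | counts |
| SAP 9.6.4, time to response | defined, Day 64 |
| SAP 9.6.5, set summarized | included |
| SAP 9.6.5, start of duration | undefined, no confirmed response |
| Protocol 8.2 | confirmation not met |

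A patient whose first PR is on the last scan collected before Amendment 9 gets the same results, for a different reason: no later assessment is in the database.

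**3. Weight of one responder.** One unconfirmed responder adds 1/25 = 4.0 percentage points to ORR in a cohort of 25, 1/50 = 2.0 in one of 50, and 1/60 = 1.7 in one of 60. These are planned cohort sizes. SAP 2.0 regroups patients for analysis, so the final denominators will differ.

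**4. Illustration under an assumed share.** Let f be the share of recorded responses that are unconfirmed. Then recorded rate = confirmed rate / (1 − f). The documents give no value for f, so 0 to 20% is an assumption. With the confirmed rate set at the null:

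| f | Cohort 1 recorded rate | P(X ≥ 28 of 60) | Cohort 2 recorded rate | P(X ≥ 6 of 25) |
|---|---|---|---|---|
| 0 | 35.0% | 0.041 | 10.0% | 0.033 |
| 5% | 0.35/0.95 = 36.8% | 0.076 | 0.10/0.95 = 10.5% | 0.042 |
| 10% | 0.35/0.90 = 38.9% | 0.135 | 0.10/0.90 = 11.1% | 0.052 |
| 20% | 0.35/0.80 = 43.8% | 0.371 | 0.10/0.80 = 12.5% | 0.083 |

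The table shows how sensitive the planning thresholds are to the definition. It does not estimate bias in this trial.

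**The case against.** The strongest reply is that the SAP is silent, not permissive. Investigators recorded response while Protocol 8.2 asked for confirmation, so the recorded CRs and PRs may already be confirmed. If so, ORR is the same under either definition. SAP 9.6.5 can also be read as treating responders as confirmed responders throughout. This stands as far as it goes: a reader might infer that the SAP deliberately counts any single CR or PR, or that ORR is shown to be inflated, and the documents support neither.

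Further points that stand:

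- The SAP has not departed from the protocol's ORR definition. Protocol 12.8 has the same unconfirmed ORR beside a confirmed duration, so the protocol disagrees with itself between 8.2 and 12.8.
- Only the Amendment 9 protocol is available. That 8.2 governed the earlier data is inferred from its note, which presents the text as retained, and from the SAP's reference to Amendment 8.
- SAP 9.0 plans no hypothesis tests. One unconfirmed response among exactly six in Cohort 2 would fall below its planning threshold, but that threshold is not applied formally and SAP 2.0 regroups the cohort.
- Biopsy of the injected lesion is not a good argument for confirmation. Tissue removed stays removed, so a repeat scan would tend to show the same shrinkage.
- A reader might see confirmed PD beside unconfirmed response as a double advantage for the drug. PD confirmation is a separate matter bearing mainly on PFS and duration, and no effect on ORR is shown.

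None of this removes the gap. If every response was confirmed, saying so costs nothing. If not, the SAP does not say which set is primary or how duration starts.

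**Conclusion.** The point holds as an unresolved inconsistency in the primary endpoint. SAP 9.6.1 and 9.6.2 set no confirmation requirement, Protocol 8.2 states one for data collected before Amendment 9, and SAP 9.6.5 needs a confirmed response to start the clock. Read literally, an unconfirmed CR or PR enters ORR with no duration start date. ORR can then be overstated, and its responders need not be the duration set.

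The direction of any error in ORR, relative to a confirmed definition, is upward or nil. Its size cannot be derived from the documents; the shares of 5% to 20% used above are assumptions. Because the analyses are descriptive, what is affected is the reported ORR and its Clopper-Pearson interval, not a formal type I error.

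**What to change.** In SAP 9.6.1 to 9.6.5:

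1. Define primary ORR as best confirmed CR or PR, using data collected before Amendment 9.
2. State the minimum interval for confirming a response. Protocol 8.2 gives none; its 4-week figure attaches to progression.
3. Use this one responder set for ORR, time to response and duration of response.
4. Report ORR including unconfirmed responses as a labelled sensitivity analysis.
5. Report separately the responders with no collected assessment after their first response, for example because collection stopped at Amendment 9, and those whose later scan failed to confirm. Scans after Amendment 9 are not in the CRF, so the first group cannot be resolved further.

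The cost is SAP wording, one sensitivity row and one short count table. Before Amendment 9 the schedule of scans every 9 weeks to Day 379, then every 12 weeks, allows confirmation without new visits. The reported ORR may be lower. Late first responders without a collected confirming scan will count as unconfirmed in the primary row, a downward effect that the sensitivity row and the separate count make visible.

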9.6.2 Best Overall Response

The best overall response rate (BORR) is the proportion of patients who achieve a best response recorded at any post-baseline assessment. BORR will be summarized and 95% Clopper Pearson confidence interval will be reported for each dose or analysis group.

9.6.3 Disease Control Rate

The disease control rate (DCR) is the proportion of patient who had CR, PR, or stable disease. DCR will be summarized and 95% Clopper Pearson confidence interval will be reported for each dose or analysis group.

9.6.4 Time to Objective Response

The time to response (TOR) will be defined as the time from the first dose of SD-101 until the onset of CR or PR. TOR will be summarized descriptively for patients who achieved CR or PR.

9.6.5 Duration of Response

The duration of response is defined as the period of time from the date of initial confirmed PR or CR until the date of PD or death, whichever is earlier. For those patients who achieved response, duration of response will be summarized descriptively. Kaplan-Meier estimate of median duration and 95% confidence interval will be provided.

9.6.6 Progression-Free Survival

The progressive-free survival (PFS) is defined as the period of time from baseline to confirmed PD or death. Administration of palliative radiation therapy will be considered clinical progression for the purposes of determining PFS. The proportion of patients who had PFS at the end of the study will be summarized and PFS will be analyzed by Kaplan-Meier method; 95% confidence interval for the median will be provided. Overall survival (OS) is defined as the period of time from baseline to death, and analysis of OS will also be provided similarly as PFS.

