4.0 ANALYSIS VARIABLES

Phase 1 – Dose Escalation

Primary Endpoints

- Incidence of DLTs
- Incidence of injection-site reactions, AEs, and SAEs
- Changes in the expression of IFN-inducible genes in whole blood (pharmacodynamic)

Exploratory Endpoints

- ORR per RECIST v1.1
- Changes in tumor-infiltrating lymphocytes, PD-L1 expression, and other gene expression in tumor biopsies (pharmacodynamic)

Phase 2 – Dose Expansion

The primary radiographic endpoints of the study will be based on RECIST v1.1 *and exploratory radiographic endpoints will be based on irRECIST (not implemented)*. All imaging endpoints for the overall response assessment will be based on investigator evaluation. A central imaging laboratory for study image collection and radiographic endpoint determination will be used per sponsor decision.

Primary Endpoints

- ORR per RECIST v1.1

Secondary Endpoints

- Incidence of injection-site reactions, AEs, and SAEs
- Time to response using RECIST v1.1
- Duration of response per RECIST v1.1
- PFS per RECIST v1.1

Exploratory Endpoints

- Changes in correlative biomarkers including tumor-infiltrating lymphocytes and PD-L1 expression at baseline and after SD-101 treatment (pharmacodynamic)
- Changes in potential tumor neoantigens in patients with recurrent or metastatic HNSCC (pharmacodynamic)

- Changes in the expression of IFN-inducible genes in whole blood in patients with metastatic HNSCC (pharmacodynamic)

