Progressive disease (PD): At least 20% increase in the sum of diameters of target lesions, taking as reference the smallest prior sum of diameters in the trial (this includes the baseline sum if that is the smallest in the trial). In addition to the relative increase of 20%, the sum must also demonstrate an absolute increase of least 5 mm.

Stable disease (SD): Neither sufficient shrinkage to qualify for PR nor sufficient increase to qualify for PD, taking as reference the smallest sum of diameters while in the trial.

Non-target lesion response assessment

Complete response (CR): Disappearance of all non-target lesions and normalization of tumor marker level. All lymph nodes must be non-pathological in size (<10 mm short axis).

Non-CR/Non-PD: Persistence of 1 or more non-target lesion(s) and/or maintenance of tumor marker level above the normal limits.

Progressive disease (PD): Unequivocal progression of existing non-target lesions. (Note: the appearance of 1 or more new lesions is also considered progression).

New lesion assessment

At each post baseline imaging timepoint, an evaluation of the presence of new lesions (yes/no) is made. The lesions are recorded as new lesions and not target or non-target lesions.

Lymph nodes must be a new lesion and measure at least 10 cm by short diameter to qualify as a new lesion overall response assessment.

A lesion identified on a follow-up study in an anatomical location that was not scanned at baseline is considered a new lesion.

Overall response assessment

Overall response assessment is based on target lesion response, non-target lesion response and new lesions and is listed in Figure 1 below.

Figure 1: Overall Response Definitions Using RECIST 1.1

Target Lesions	Non-target Lesions	New Lesions	Overall Response
CR	CR	No	CR
CR	Non-CR/non-PD	No	PR
CR	Not evaluated	No	PR

PR	Non-PD or not all evaluated	No	PR
SD	Non-PD or not all evaluated	No	SD
Not all evaluated	Non-PD	No	NE
PD	Any	Yes or No	PD
Any	PD	Yes or No	PD
Any	Any	Yes	PD

CR = complete response; NE = not evaluable; PD = progressive disease; PR = partial response; SD = stable disease.

Approved

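### SAP 9.6.6 labels PFS as RECIST v1.1 but counts radiographic progression only once confirmed; it also plans a PFS proportion that depends on follow-up and an OS curve without scheduled survival follow-up

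*SAP*

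**What the plan says.** SAP 4.0 lists "PFS per RECIST v1.1" as a Phase 2 secondary endpoint. In the same section it says "exploratory radiographic endpoints will be based on irRECIST (not implemented"). SAP 9.6 repeats that irRECIST is not implemented, then states as an adaptation of RECIST v1.1: "Determination of progressive disease (PD) requires a confirmation of PD by imaging" at least 4 weeks later. It adds an exemption: "Patients that are deemed clinically unstable are not required to have repeat imaging for the confirmation of PD".

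SAP 9.6.6 then says PFS "is defined as the period of time from baseline to confirmed PD or death", with palliative radiotherapy also counted as progression. SAP Appendix 1 defines target-lesion PD as "At least 20% increase in the sum of diameters of target lesions, taking as reference the smallest prior sum of diameters in the trial", plus a 5 mm absolute increase, with no confirmation step. SAP 9.6.5 ends duration of response at PD without the word confirmed.

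On reporting, SAP 9.6.6 says: "The proportion of patients who had PFS at the end of the study will be summarized and PFS will be analyzed by Kaplan-Meier method". Its last sentence defines OS and says "analysis of OS will also be provided similarly as PFS". OS is not an objective or endpoint in either document.

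SAP 8.0 places the final analysis after the last participant's last visit. The SAP gives no censoring rule for PFS, duration of response or OS, and no efficacy data cut-off. It is written to protocol Amendment 8. Protocol 4.3.2.2 says radiographic PFS is not collected as of Amendment 9.

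**The concern.** There are three separate problems.

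1. **Label and definition disagree.** Protocol 8.2.1.1 describes confirmation of PD as the primary difference between irRECIST and RECIST v1.1. The SAP therefore applies the defining rule of a criterion it does not implement to an endpoint named for the other criterion. It does not say whether confirmed PD is dated at the first or the confirming scan, how a PD that is never confirmed is handled, or whether single-scan PD in a clinically unstable patient is a PFS event. A reader could not tell how far the reported PFS lies from RECIST v1.1 PFS.

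2. **The crude proportion measures follow-up as well as PFS.** SAP 2.0 shows results by 2 mg and 8 mg. If the two groups were observed for different lengths of time, the proportions differ even when PFS is identical.

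3. **OS has no follow-up behind it.** If observation ends soon after treatment stops, and treatment stops largely because of progression, censoring is tied to prognosis. Kaplan-Meier assumes that it is not.

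**Working it through.** The documents state no expected PFS or OS, so there is no planned figure to reproduce. The sizes below rest on assumptions, which are given with each step.

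**Step 1: direction of the PFS difference.** Compare PFS to first PD with PFS to confirmed PD, counting deaths and radiotherapy the same way. Every confirmed PD was first a PD. Patient by patient, the confirmed event falls on the same date, falls later, or is lost. Time to the event is therefore equal or longer, never shorter.

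**Step 2: illustrative size.** Scans fall at Days 64, 127, 190 and so on (Protocol 8.2.1.2). Assume exponential PFS with a median of 4 months (4 × 30.4375 = 121.75 days). The share with PD found at each scan is:
- q1 = 1 − 2^(−64/121.75) = 0.305
- q2 = 1 − 2^(−63/121.75) = 0.301

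The last scan before six months (Day 182.6) is Day 127. Let u be the share of PDs never confirmed and censored at the PD scan.

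| Rule | Formula | u = 0 | u = 10% |
|---|---|---|---|
| First PD (reference) | (1−q1)(1−q2) | 48.5% | 48.5% |
| Confirmed, dated at first scan | (1−(1−u)q1)(1−(1−u)q2) | 48.5% | 52.8% |
| Confirmed, dated 28 days later | product of (1−q)/(1−uq) | 48.5% | 51.6% |
| Confirmed, dated at next scheduled scan | (1−q1)/(1−u·q1) | 69.5% | 71.7% |

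The 28-day row equals the reference at u = 0 only at this landmark. Each event is still dated 28/30.4375 = 0.9 months later. The next-scan row is large because a PD found at Day 127 is not dated until Day 190, after the landmark.

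**Step 3: crude proportion.** With no drop-out, the share event-free after t months is 2^(−t/median). For a median of 4 months it is 35%, 13% and 2% at 6, 12 and 24 months. For a median of 9 months it is 63%, 40% and 16%.

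According to the Protocol 4.1 footnotes, Cohorts 1 to 4 closed at Amendment 6, when Cohorts 5 to 7 (2 mg) opened. Cohort 8 (2 mg) opened at Amendment 7. Assume identical true PFS, with 9 months of follow-up for 2 mg and 18 months for 8 mg:

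| Median PFS (months) | 2 mg at 9 months | 8 mg at 18 months | False difference (points) |
|---|---|---|---|
| 4 | 21.0% | 4.4% | 16.6 |
| 6 | 35.4% | 12.5% | 22.9 |
| 9 | 50.0% | 25.0% | 25.0 |
| 12 | 59.5% | 35.4% | 24.1 |

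If half the 2 mg group also had 18 months, each difference halves, to about 8 to 12 points.

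**Step 4: length of observation.** Screening of 28 days, the last scheduled pembrolizumab on Day 715 and the visit 28 days later give (28 + 715 + 28)/7 = 110.1 weeks. Protocol 4.2 states about 110 weeks. No survival period fits within that.

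**Step 5: OS.** Assume a median PFS of 4 months, a median survival after progression of 9 months, and 5% of first events being deaths. With a = ln2/4 and b = ln2/9:

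True 12-month OS = e^(−12a) + 0.95 × a/(a−b) × (e^(−12b) − e^(−12a)) = 0.125 + 0.95 × 1.80 × (0.397 − 0.125) = 59%.

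Simulation of 400,000 patients, with exit a fixed time after the PD scan, gives this Kaplan-Meier 12-month OS:

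| Later deaths recorded | Exit 28 days | 56 days | 90 days | 118 days |
|---|---|---|---|---|
| None | 74% | 70% | 66% | 64% |
| Half | 63% | 62% | 61% | 61% |
| All | 59% | 59% | 59% | 59% |

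Confirmation at 28 days plus the 28-day visit corresponds to about 56 days.

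**The case against.** The strongest reply is that SAP 9.6 says openly that it adapts RECIST v1.1, in terms taken from Protocol 8.2.1.1. The rule is pre-specified and visible. That is true, and it makes the conflict one of labelling and missing detail; nothing is concealed. It still stands, because SAP 4.0 and Appendix 1 tell the reader something else and no dating rule is given.

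Four stronger readings are tempting, and the documents do not support them.

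- **That reported PFS will exceed RECIST v1.1 PFS by 20 points or more.** This needs dating at the next scheduled scan, which no section states. It also depends on the landmark, and the SAP plans a median and a crude proportion, with no six-month estimate. The loss of unconfirmed PDs may be overstated too, since Protocol 8.2 lets stable patients whose PD is not confirmed continue on the scan schedule, where later events can count. Nor is the SAP's PFS shown to be longer than strict radiographic PFS: the radiotherapy event lies outside RECIST and can shorten it.
- **That single-scan PD in unstable patients never counts.** SAP 9.6 exempts them from repeat imaging. Whether their PD is an event is simply not stated.
- **That the dose comparison is distorted by 17 to 25 points.** That gives every 2 mg patient the short follow-up. SAP 2.0 pools early 2 mg patients from Phase 1 and Cohort 1 into the melanoma groups and lists some in Cohorts 2 to 4. The documents do not date Amendment 9, so 9 and 18 months are assumptions. A Kaplan-Meier analysis is also reported alongside.
- **That no later deaths are known.** Protocol 11.0 asks for deaths on CRFs, and SAE reporting runs to 90 days or longer in some cases. Treatment after confirmed PD is also contemplated in Protocol 9.2, so exit need not follow progression closely.

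Two limits also apply. The follow-up text is that of Amendment 9, whereas the SAP cites Amendment 8, which is not available; the Phase 1 schedule likewise shows no survival visits. Amendment 9 also limits Phase 2 to selected analyses, so the point concerns whatever PFS or OS is reported.

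**Conclusion.** The point holds as a defect of definition. PFS as defined in SAP 9.6.6 is not the endpoint named in SAP 4.0. Against PFS to first PD with the same death and radiotherapy events, it is equal or longer by an unknown amount, which is zero if PD is dated at the first scan and every PD is confirmed.

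The crude end-of-study proportion depends on follow-up and can favour 2 mg. The early 2 mg patients dilute this, to about half the illustrated gap if they make up half the group.

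OS is unlisted. With no survival visit after the one 28 days after last dose, its Kaplan-Meier curve is likely to be too high unless later deaths are captured. In the illustration the excess at 12 months runs from nothing to 15 points.

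Confidence is high on the wording and low on the sizes, which rest on assumed medians, confirmation rates and follow-up. PFS is secondary and everything is descriptive, so this should be fixed but threatens no formal test.

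**What to change.** 1. In SAP 9.6, 9.6.5 and 9.6.6, define PD as the first PD per RECIST v1.1, dated at that scan. Run PFS from the first dose of trial treatment to that PD, death or palliative radiotherapy (the rule already in 9.6.6), whichever comes first. State this origin in place of baseline, which SAP 7.1 defines only as a value; it matters because Cohorts 1 and 3 start SD-101 on Day 22. Keep confirmed-PD PFS only as a labelled sensitivity analysis that states its dating rule and whether single-scan PD in unstable patients counts.
2. Replace the crude proportion with Kaplan-Meier PFS at stated landmark times with 95% confidence intervals. Censor patients without an event at the last tumour assessment collected before Phase 2 efficacy collection stopped, and give that date.
3. Drop the Kaplan-Meier OS analysis, or report captured deaths as on-study deaths only.

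The cost is SAP wording and programming, with no new data. The downside for the sponsor is less favourable PFS figures and no OS curve.
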